### **Data Analysis Plan**

All data will be initially tested for normality, outliers, and errors. We will then compute summary statistics and derive across-group statistical comparisons to identify any demographic variables, such as age, gender, education, or cognitive frailty, group differences after the randomization process. If group differences are detected for a variable, all analyses will include that variable as a covariate. We will also present primary and secondary outcome measures using descriptive statistics, summarize categorical variables using frequencies and proportions, and report descriptive statistics as medians and interquartile ranges.

***Analyses of Primary and Secondary Cognitive Outcomes.*** Outcomes will be tested according to the intention-to-treat principle with analysis of variance, evaluating both the changes from baseline to the completion of training (immediate treatment effects) and the changes from baseline to +6mo after training (retention effects). All analyses will be conducted on the baseline-normed Blom transformed scores for each measure, an approach used in prior intervention research on older adults. Composite cognitive scores (for each cognitive outcome) will be formed by averaging these scores. Therefore, we shall conduct all statistical analyses on one composite cognitive score representing the primary outcome (episodic memory) and one composite score representing the secondary outcome. There will be, for both outcomes, three composite scores- one for each Assessment (A, B and C). Specific Aim 1 focuses on the increases in cognition between the three training arms at both immediate post-testing and +6mo period. Change scores for each composite score for each individual will first be plotted to evaluate the treatment-related cognitive benefits. We will then examine the composite scores for the primary outcome using repeated measures ANOVA, with Training Arms (3: Low-C, High-C, High-C+) as a between-subject factor and Assessment (2) as a within-subject factor, for both immediate post-training gains (Assessments A and B) and for long-term retention of these gains (Assessments A and C). Of main

interest is the interaction between the Training Arms and Assessments. To evaluate the extent of immediate post-test cognitive gains across the three training arms, we will conduct pairwise contrasts between High-C and High-C+. Similar analysis will be conducted for the secondary outcome. The two ANOVAs will be adjusted to  $p < .025$  ( $= .05/2$ ) to adjust for multiple comparisons.

Additional analyses will investigate how *cognitive frailty*, as measured by MOCA and MMSE, interacts with training difficulty (High-C vs. High-C+) and extent of transfer, because cognitively fit older adults show faster learning rates for complex skills and working memory. We predict that older adults with greater cognitive frailty will exhibit less cognitive plasticity and therefore will benefit most from moderate attentional control training (High-C), whereas older adults with higher cognitive functioning will find the most challenging training dose (High-C+) to be most beneficial and exhibit greatest cognitive plasticity.

***Analyses of Primary and Secondary Neuroimaging Outcomes.*** There are two main fMRI tasks of interest- one for primary cognitive outcome (episodic memory), called *subsequent memory*; another for secondary cognitive outcome (executive control), called *task-switching*. An additional fMRI task, *working memory updating*, a near transfer task for all arms, will also be evaluated. For each task, we will derive a summary BOLD measure that best characterizes neural activity for the task after correcting for multiple comparisons. Those summary values will be entered into an ANOVA, where the Training Arm (3: Low-C, High-C, High-C+) x Assessment (pre-test vs. post-test) interaction will be evaluated, followed by post-hoc analyses of these interaction effects. We will also calculate group differences in the contrasts of interest at the post-test scans. The critical contrasts of interest for the subsequent memory is Remembered vs. Forgotten items, and for task-switching is Dual vs. Single task. The resulting ROI clusters, after correcting for multiple comparisons, will be used to extract percent signal change for all individuals at both pre-test and post-test. Specific Aim 2 evaluates whether the post-training changes in fronto-parietal activations are largest in the High-C and High-C+, compared to the Low-C, training arms. The percent signal change data will be submitted to a Training Arm x Assessment ANOVA, which will be followed by planned-comparisons between the groups to evaluate the specific aim 2. These interaction effects will be conducted for all task difficulty conditions in the fMRI tasks, because post-intervention activation patterns are hypothesized to be different for simpler conditions (e.g., 0-back; Single task; water present) compared to the more difficult conditions (e.g., 3- back, Dual task; water absent) of the fMRI tasks. We will also calculate task-specific activations for difficult vs. simpler condition contrasts (e.g., 3-back>0-back; Dual>Single; water absent>water present) in younger adults (YA), after correcting for multiple comparisons. The resulting ROI

clusters from YA will be used to extract percent signal change for all older individuals (OA) at both assessments. A univariate ANOVA with 3 groups (post-test Low-C, post-test High-C+, and YA) will be conducted to evaluate whether the post-test activations in High-C+ older adults in these task-related regions are closest to that of YA. We predict that for the primary (subsequent memory) and secondary (task-switching) outcomes, High-C and High-C+ older adults at post-training will have increased task-related neural activations mimicking that of younger adults, and reduced non-compensatory over-activations compared to baseline.

For the network analyses, we will utilize seed-to-voxel based connectivity from the major nodes within two cognitive networks, Fronto-Parietal (FP) and Cingulo-Opercular (CO), at both pre- and post-testing sessions. Changes in post-training functional connectivity in these two networks will be evaluated at all task difficulty conditions for memory updating (0-back, 3-back), task switching (single task, dual task), and subsequent memory task (water present, water absent). The interaction effects will help evaluate whether the connectivity of attentional networks change most for the higher attentional control training groups. We will also conduct separate pair-wise comparisons between High-C and High-C+ for both primary (*Subsequent Memory*) and secondary (*Task Switching*) cognitive outcomes, corrected for multiple comparisons, to determine if High-C+ engenders most neural changes.

**Other neuroimaging analyses.** For structural data, gray matter volumes of fronto-parietal and subcortical regions from FreeSurfer parcellations as well as white matter integrity Fractional Anisotropy (FA) maps from pre-test, along with cognitive scores at pre-test, will first be subject to a Multiple Factor Analyses using the ExPosition package for R to reduce the number of brain regions for future analyses. Significance of resulting components, via 1000-iteration permutation test, and component contributors, via 1000-iteration bootstrap test, will be assessed. The volumes and FAs of *only* the significant components, as well as specific ROIs that have been linked to game learning or cognitive control (e.g., right cingulum/hippocampus FA, genu FA, striatal volume), will then be entered into a Training Arm (3: Low-C, High-C, High-C+) x Assessment (pre-test vs. post-test) ANOVA to evaluate training-related structural changes in both gray matter volume and white matter integrity. We will also calculate correlations between changes in brain function, changes in brain structure and cognitive gains in primary and secondary outcomes for all training arms. We expect greater coupling of changes in brain and changes in cognition in the high attentional control training arms (High-C and High-C+) compared to the Low-C training arm.

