Arm 1: Low Attentional Control Group (Low-C). Low attentional control training using an n-back simulation game (*Birdwatch*), requiring predictable shifts of cued-attention. Arm 2: High Attentional Control Group (High-C). High attentional control training using the *Birdwatch* simulation game, requiring unpredictable shifts of cued-attention. Arm 3: Highest Attentional Control Group (High-C+). This arm uses a commercial strategy video game for training (*Sushi Chef*), rather than the experimenter-developed simulation games proposed in the other two arms. Additionally, a *comparison group of younger adults (YA)* will undergo pre-screening, mock scan, and MRI scan sessions (but no training). All older participants will undergo 3 behavioral assessment sessions, each lasting a maximum of 3.5 hours, in the PI's lab. These assessments will be conducted at baseline, immediately post-training and 6 months after completion of training. All older adults will also undergo 2 neuroimaging assessments, one at baseline, and another at immediate post-training. There will no more than 5-day difference between the MRI scan and the respective behavioral assessment at either baseline or at immediate post-training.

The training period will last for 19 h over 8 weeks, and will include both in-lab and at-home training on a device provided to the participant. All training will be administered individually to the participant, not in a group. Fig. 5 and Fig. 6 show the computerized games used in the three training arms.

***Screening and Randomization.*** In this individually randomized trial, all interested participants will first be prescreened and will undergo a Mock Scan session to determine their eligibility to participate in the study. Participants will be consented to screening for eligibility. In order to exclude participants with memory-related disorders, primarily MCI and AD, participants will be required to have both a Mini-mental Status Examination (MMSE) score of 26 or greater, and a

Montreal Cognitive Assessment (MoCA) score of 24 or greater. A composite of these two standardized scores will comprise an index of *cognitive frailty*. The cutoff scores are conservative and should screen out most cases of MCI, although we acknowledge that some early stage MCI individuals could still be included. Additionally, brain scans will be screened by a neuroradiologist if a pathology is suspected.

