If after the pre-screening and the Mock Scan sessions, a volunteer meets the inclusion and exclusion criteria, he or she will be randomized into one of the three training arms. This assignment will be based on a random computerized allocation plan, where the average cognitive frailty, age, education and gender distribution will be maintained to be equivalent across the three arms. By randomly assigning participants in the training arms and by assessing outcomes by blinded experimenters, we will avoid selection bias and outcome assessment bias. The power analyses for sample size justification, therefore, is for this individual randomized trial, where Type 1 and type II errors are defined, expected meaning difference between the experimental groups and Low-C are specified, and attrition is estimated at follow ups. The participant will need to be randomized to a training arm prior to any baseline assessments.

***Minimizing Attrition and Enhancing Adherence.*** Attrition at follow ups will be minimized because in addition to the weekly in-lab training, there will be weekly at-home training where the participants can conduct the training from the comfort of their home during their preferred time on the device (Windows tablet) provided to them. Compliance for at-home sessions will be measured by the device's time stamp, which will be recorded every time the participant logs into the training program. Participants will also be provided with a diary to keep a log of their training schedule to enhance compliance. Moreover, participants will be encouraged to call researchers of the unblinded, training group with any questions about the game. The weekly in-lab testing will ensure that any difficulties participants may encounter during at-home training is resolved.

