***Sample Size Justification for the older adults in the RCT.*** We estimated the power (using G\*power3.1) to detect the differences between the Training Arm (3) x Assessment (2) interaction on the primary cognitive outcome. *The current study is the first phase of a larger randomized controlled trial. We calculate our power for the full trial, but our requested sample size for this study is 51.* We will recruit 177 older adults with the aim to retain a total sample size of 144 older adults at immediate post-training with the expected attrition of 18%. We report two expected effect sizes of Cohen's *f* for our calculations. One,  $f=.35$ , the minimum effect size obtained across our 3 pilot studies. Another,  $f=.16$ , based on a meta-analysis on computer-based cognitive training in older adults. The proposed total sample size of 144 older adults will provide us with >93% power to detect the Training Arm (3: Low-C, High-C, High-C+) x Assessment

(A vs. B) interaction at  $f=.16$  and  $>98\%$  power to detect the interaction at  $f=.35$  on the primary cognitive outcome at  $p<.05$ . It will also provide  $>90\%$  power to detect a meaningful between-group difference ( $f=.35$ ) at immediate post-testing, after controlling for baseline cognition, at  $p<.05$ . At +6mo retention period (Assessment C), we expect to retain a total of 117 older adults, after the expected  $\sim 20\%$  attrition between Assessments B and C. This will provide us with  $>87\%$  power to detect the Training Arm (3: Low-C, High-C, High-C+) x Assessment (2: A vs. C) interaction at  $p<.05$  at  $f=.16$ . We will conduct 2 ANOVAs, one for primary and one for secondary. Our proposed sample size will provide us with sufficient power ( $>87\%$ ) to detect the Training Arm (3) x Assessment (2) interaction at a corrected  $p$  value of .025 ( $=.05/2$  for 2 cognitive outcomes of interest).

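### Covariates depend on a post-randomization test of factors that allocation already balances, and the change-type primary test is valid but usually less precise than fixed adjustment for the baseline composite

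*Combined protocol and SAP*

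**What the plan says.** Under Screening and Randomization, a computerized plan allocates so that "the average cognitive frailty, age, education and gender distribution will be maintained to be equivalent across the three arms". Frailty is built from the MMSE and MoCA screening scores. Allocation comes first: "The participant will need to be randomized to a training arm prior to any baseline assessments". The Assessment A composite therefore cannot be an allocation factor.

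The Data Analysis Plan then compares the arms statistically to "identify any demographic variables, such as age, gender, education, or cognitive frailty, group differences after the randomization process", and continues: "If group differences are detected for a variable, all analyses will include that variable as a covariate". No test, threshold or closed list of variables is given.

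The primary cognitive analysis is a repeated measures ANOVA with three arms and two assessments (A and B, then A and C). Of main "interest is the interaction between the Training Arms and Assessments". Each of the two ANOVAs, one per cognitive outcome, is tested at .025.

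The Sample Size Justification also claims more than 90% power at f=.35 for a between-group difference "at immediate post-testing, after controlling for baseline cognition". Frailty has a separate role as a moderator in the additional analyses: "We predict that older adults with greater cognitive frailty will exhibit less cognitive plasticity".

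**The concern.** Three things do not fit together.

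- **The rule.** After random allocation, an arm difference in age, gender, education or frailty is chance. Testing for it is not a sound basis for choosing covariates, and the open list lets the observed data settle the model. The plan also does not say how a covariate would enter. Added to a repeated measures ANOVA as a main effect only, it cannot change the interaction test at all.
- **The baseline composite.** This is usually the most prognostic variable available and is already collected, but it enters only through the change score, which fixes its coefficient at 1 rather than estimating it.
- **The power statement.** The power claim that controls for baseline cognition has no counterpart among the cognitive analyses.

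At stake are precision in a 30-person phase and a primary model that can be written down before data are seen.

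**Working it through.** **Inputs.** f=.16, f=.35, N=144 and N=117 (Sample Size Justification); 30 retained (Study Design, Overview); alpha .025 (analysis plan). Rho and the SDs are not stated, so rho is varied from .5 to .9.

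**1. Reproducing the plan's figures.** For the interaction, lambda = f² × N × 2/(1−rho), with df 2 and N−3. At rho .5 and alpha .05:
- N=144: lambda = .0256 × 144 × 2/.5 = 14.75, power .935 (stated >93%).
- N=117: lambda = 11.98, power .874 (stated >87%).
- Baseline-controlled comparison, f=.35, N=144: lambda = f² × N = 17.64, df 2 and 140, power .969 (stated >90%).

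So rho .5 fits the stated interaction figures, although no document states it.

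**2. Change against adjustment.** Set the SD at A to 1 and the SD at follow-up to k. The change score has variance 1 + k² − 2k·rho; the baseline-adjusted outcome has k²(1−rho²). The difference is (1−k·rho)², never negative. In large samples adjustment cannot be less precise. With k=1 the ratio is (1+rho)/2: .75, .85, .90 and .95 at rho .5, .7, .8 and .9. Chance baseline imbalance multiplies the adjusted variance by about 1 + 1/(N−5), which is 1.04 at N=30, and one df is lost. Break-even at N=30 is rho = 2 × 25/26 − 1 = .92.

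**3. Power at N=30, f=.16, alpha .025, equal SDs.**

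| rho | lambda, planned | power | lambda, adjusted | power |
|---|---|---|---|---|
| .5 | 3.07 | .20 | 3.94 | .26 |
| .7 | 5.12 | .35 | 5.79 | .40 |
| .8 | 7.68 | .53 | 8.21 | .56 |
| .9 | 15.36 | .86 | 15.55 | .87 |

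Without the imbalance penalty the adjusted figure at rho .5 is .27. Simulation (three arms of 10, equally spaced effects) agrees.

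**4. Unequal SDs (simulated, planned vs adjusted, rho .5/.7/.8/.9).**
- k=1.1: .183 vs .217, .307 vs .326, .464 vs .459, .801 vs .783.
- k=1.25: .153 vs .168, .256 vs .249, .379 vs .365, .658 vs .662.
- k=0.9: .230 vs .338, .382 vs .493, .563 vs .668, .884 vs .933.

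The largest loss is about .02; the gain grows if the SD falls.

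**5. How often the rule would act.** At an assumed 5% level, four independent tests with no balancing give 1 − .95⁴ = .185. In simulated allocations balanced on the four factors, the rule fired in 0% (best of 200 allocations) or about 2% (minimization) of trials.

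**6. Does allocation already balance the baseline composite?** Only slightly. With 10 per arm, simple randomization gives a two-arm difference with SD √(2/10) = .447. Balancing frailty lowers this only to .426 or .406 at an assumed frailty-composite correlation of .5 or .7.

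**7. Adding all four factors as well.** Residual df fall from 27 (planned) to 22. If the factors explain nothing, planned vs full model at rho .5 is .207 vs .250 (tight balancing) or .199 vs .232 (minimization). At rho .9 it is .864 vs .842 or .862 vs .818, a loss of .02 to .04. At 6 months, applying the plan's roughly 20% attrition, 30 × .8 = 24 and df fall from 21 to 16. Simulations at rho .9 gave .724 vs .655 and .747 vs .672, a loss of about .07. Baseline alone at N=24 gives, by the formula in step 2, .154 to .195 at rho .5 and breaks even at rho = 2 × 19/20 − 1 = .90.

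**The case against.** The strongest reply is that nothing is broken. Outcome, model, interaction and alpha are pre-specified; baseline is used through change, which is how the plan frames its question; and the covariate rule looks at baseline characteristics, not outcomes. This stands as far as validity goes. A reader might infer a biased test or inflated type I error. The documents do not support that: the simulated size of the planned test at nominal .025 was .019 to .030.

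Second, the gain depends on rho, the SD ratio and the meaning of f. With f in the interaction metric and equally spaced arms, the arm means lie at −m, 0 and +m with m² = 6 × .16² = .154. That puts Low-C and High-C+ .78 SD apart, which is large. If .16 were instead the SD of arm means at follow-up, power at N=30 would be only .06 vs .07 at rho .5 and .13 vs .14 at .8. This also stands; the figures above use the metric that reproduces the plan's own numbers.

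Third, the rule might seem likely to reshape the model often. The 18.5% figure ignores the balancing that the protocol describes, so it is an upper reference, not an expectation.

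Fourth, a reader might take the words about all analyses to force an age covariate into the ANOVA with younger adults. The rule concerns differences after randomization, younger adults are not randomized, and balancing makes a trigger on age rare. That reading is too strained to be a ground for this point.

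The objection does not answer the missing baseline-controlled analysis or the undefined covariate set. Neither depends on rho.

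**Conclusion.** The point holds as one of pre-specification and efficiency, not validity; severity is minor to moderate. The covariate rule should go because it leaves the model open, even though it would seldom act. Adjusting for the Assessment A composite is usually better than the change test. At N=30 it adds about .06 power at rho .5, .05 at .7 and .03 at .8, and essentially nothing at .9, assuming equal SDs and f=.16 in the plan's interaction metric. A loss of about .02 is possible if the SD rises after training. It also supplies the analysis that the sample-size section already powers. A reader might conclude that all four allocation factors belong in the model by default. In so small a phase the working does not support that, because at high rho the full model can do worse than the planned test.

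**What to change.** - Delete the test-triggered rule and report baseline comparisons descriptively.
- Make the primary cognitive analysis the composite at B, and separately at C, regressed on arm and the Assessment A composite, with the arm test at .025. Do the same for executive functions. Refer the baseline-controlled power statement to this analysis.
- In this phase, let the baseline composite be the only default covariate. Any allocation factors to be added should be a short list fixed before data are seen, or used in a sensitivity analysis.
- Keep the Arm by Assessment ANOVA as a supporting analysis, and keep the frailty-by-training analysis separate.
- For imaging, state that the post-test group comparisons adjust for the pre-test value and that the deleted rule no longer applies. Episodic memory fMRI is a primary outcome. With equal SDs, that adjustment multiplies the variance by 1−rho²: .91, .75 and .51 at rho .3, .5 and .7.

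The cost is SAP wording, one residual degree of freedom (27 to 26 at N=30) and the possible small loss if the SD rises after training. No new data are needed.

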### **Study Design**

**Overview.** This parallel arm, individually randomized control trial (RCT) will recruit 34 older adults from Dallas and neighboring counties. We aim to retain at least 30 participants on whom immediate post-training gains in both *near* and *far* abilities can be observed. This RCT shall be registered at [ClinicalTrials.gov](https://clinicaltrials.gov). There will be a Clinical Coordination Team (co-directed by [name] and the Project Manager) that will implement the intervention and check in with the participants on a weekly basis regarding their training progress. A blinded data collection team, directed by a post-doctoral fellow, will collect both behavioral and neuroimaging assessments before and after training. There will also be

a Data Coordination Team (co-directed by [name] and a post-doctoral fellow) that will be responsible for scoring and preprocessing the data. All data will be deposited in a HIPAA compliant server at the PI's laboratory. The team leaders will meet twice a month and each team will meet weekly to oversee any issues with subject recruitment, logistics and data collection. We will also recruit a total of 20 younger adults (YA, 18-30 years of age) for neuroimaging, who will be the functional controls for the older adults in the RCT.

This is a Phase 1 trial with multiple interventions in older adults, where the goal is to compare high attentional control trainings (High-C and High-C+) to low attentional control training (Low-C) and evaluate training-related changes in neurocognitive functions of both near (secondary outcome) and far transfer (primary outcome) tasks.

***Experimental Design.*** There are three intervention arms for older adults (OA) in this RCT trial, where attentional control demands in working memory training will be systematically increased using engaging game-based simulations.

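### The two-visit ANOVAs of the cognitive composites forgo a baseline adjustment that the sample size section itself powers, and the six-month test leaves out people whose Assessment B scores are in hand

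*Combined protocol and SAP*

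**What the plan says.** In the Data Analysis Plan, under Analyses of Primary and Secondary Cognitive Outcomes: "Outcomes will be tested according to the intention-to-treat principle with analysis of variance". The model is then named: "We will then examine the composite scores for the primary outcome using repeated measures ANOVA", with three arms and two assessments, "for both immediate post-training gains (Assessments A and B) and for long-term retention of these gains (Assessments A and C". The interaction is the effect of main interest, the secondary composite is treated the same way, and each outcome is tested at .025 (.05/2).

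In Study Design, the sample size justification quotes more than 93% power for the A-B interaction (N=144) and more than 87% for the A-C interaction (N=117), both at f=.16 and alpha .05. It also quotes more than 90% power at f=.35 for a group difference "at immediate post-testing, after controlling for baseline cognition".

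The analysis plan has no baseline-adjusted test of the composites. Its only planned post-test group comparison concerns imaging: "We will also calculate group differences in the contrasts of interest at the post-test scans". Demographic variables and cognitive frailty become covariates only when the arms are found to differ on them after randomisation, although the allocation scheme already balances these variables. Cognitive frailty is an MMSE/MoCA screening index, not the baseline composite.

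On loss to follow-up, the full trial is to "retain a total sample size of 144 older adults at immediate post-training with the expected attrition of 18" per cent, with about 20% further "attrition between Assessments B and C". For this phase, 34 are recruited, and the Overview says "We aim to retain at least 30 participants on whom immediate post-training gains" can be observed. Nothing states how missing assessments are handled or what is assumed about them.

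**The concern.** There are two linked issues and one secondary one.

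- **Precision.** A two-visit interaction fixes the slope of follow-up on baseline at 1. Estimating that slope uses the Assessment A composite better at low to moderate correlation. In a trial of about 30, precision is scarce, and the sample size section already refers to such an analysis.
- **Retention at six months.** An ANOVA on A and C needs both scores, so someone seen at A and B but not C drops out of it. If loss related to gain at B differs between arms, the comparison of those who return is distorted, although the B scores that could reduce the distortion are held.
- **Covariates (secondary).** Choosing covariates by a post-randomisation check means that the model is not fixed in advance.

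**Working it through.** **Inputs.** From the documents: f=.16 and f=.35; N=144 and 117 (full trial); 34 recruited and 30 retained (this phase); losses of 18% and about 20%; alpha .05 for the quoted powers and .025 for the tests. Assumed: pre-post correlation ρ, which is not stated, and equal variances at each visit. The sample size section also gives 51 for this study; the Overview's 30 is used, with 51 shown once.

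**Reproducing the plan's power.** For the interaction, λ = 2Nf²/(1−ρ), with df 2 and N−3. At ρ=.5:
- N=144: λ = 2×144×.0256/.5 = 14.75, power 93.5% (stated >93%).
- N=117: λ = 11.98, power 87.4% (stated >87%).

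So ρ of about .5 fits the quoted figures. The adjusted post-test claim has λ = Nf² = 144×.1225 = 17.64, df 2 and 140, giving 96.9%, consistent with >90%.

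**Effect of baseline adjustment.** For the same mean differences, adjusted variance divided by change-score variance is (1−ρ²)/[2(1−ρ)] = (1+ρ)/2. So λ is multiplied by 2/(1+ρ), with df 2 and N−4. At N=30, f=.16, ρ=.5, λ rises from 3.07 to 4.10, and the formula gives 20.2% and 27.3%. It ignores the cost of estimating the slope, so simulated values are used below (N=30, f=.16, alpha .025):

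| ρ | change score | baseline-adjusted |
|---|---|---|
| .3 | 14% | 21% |
| .5 | 20% | 26% |
| .7 | 35% | 39% |
| .8 | 53% | 56% |
| .9 | 86.5% | 86.8% |

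At ρ=.5, 30 people analysed with adjustment are worth about 38 by change score (43 at .3, 34 at .7). With N=51, power goes from 38% to 50%. At f=.35 on the same interaction scale, N=30, ρ=.5, it goes from 84.6% to about 93%.

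**Numbers at C.** 30×.8 = 24. With the full-trial loss of 18%, 34×.82 ≈ 28 at B and 28×.8 ≈ 22 at C. The A-C test then omits 10 to 12 of 34 (29-35%). About 6 of these have A and B scores. The other 4 to 6 (34−30 or 34−28) were lost before B and, if they do not return, have no follow-up score.

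**Bias in the A-C arm comparison (illustration, no true effect).** Assume 10 per arm at B and the same correlation ρ between every pair of visits. The A-B gain has SD √[2(1−ρ)], and the regression of A-C change on A-B gain has slope ½. Dropping an arm's k smallest gains shifts its mean A-C change by ½√[2(1−ρ)]·m(k), where m(k) is the expected mean standardised gain of those kept. From normal order statistics for 10 (1.539, 1.001, .656, .376): m(2) = 2.540/8 = .318, m(3) = 3.196/7 = .457, m(4) = 3.572/6 = .595. Results are in SD units for ρ = .3, .5, .7:
- Every arm loses its 2 smallest gains: the shifts cancel and the bias is zero.
- Losses of 2, 2 and 3 by the same rule: ½√[2(1−ρ)]×.139 = .08, .07, .05.
- Extreme case (4 smallest gains lost in one arm, 1 at random in each other arm): simulated .36, .29, .23 (the formula gives .35, .30, .23). A likelihood estimate using B is within .01 of zero. Baseline adjustment in completers alone still leaves about .15 at ρ=.5.

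**The case against.** The strongest reply is that the planned test is not wrong. A change-score comparison is valid under randomisation, and at f=.16 the gain is only about 3 to 7 points over ρ of .3 to .8 and nil at .9. The value ρ=.5 comes from reading quoted lower bounds as near-exact. Using B scores also hardly improves precision at C when loss is random (SE .444 against .446 SD at ρ=.5). All of this stands: the precision point concerns efficiency, and the case for using B is a weaker missing-data assumption.

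Three stronger readings are tempting and are not supported.

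- A reader might infer that any loss related to gain at B biases the retention result. For the arm comparison it does not: with no true effect, the same pattern in every arm gives no bias. Loss must differ by arm, and nothing in the documents says that it will.
- A reader might infer that power in this phase is low whichever model is used. That holds at f=.16. At the plan's f=.35 on the interaction scale, the planned ANOVA already has about 85% power at N=30 and ρ=.5. If f=.35 is read instead as a direct baseline-adjusted post-test effect, power at N=30 and alpha .025 is about 24%, so the answer depends on effect size and scale.
- A reader might take the omission of people lost after B as a stated rule. It is an inference from the form of the model, supported by the A-C power being computed on the 117 expected at C.

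**Conclusion.** The point holds as an improvement that should be made, not as an error of validity. Two parts rest on the text alone: the sample size section powers a baseline-adjusted comparison that the analysis plan lacks, and intention-to-treat is declared with no missing-data assumption although about a third of those recruited are expected to be absent at C (177 to 117, 33.9%).

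The size of the precision gain depends on the assumed ρ and equal visit variances; it disappears at about .9. The size of any retention bias cannot be derived from the documents: the illustrations run from zero, through .05-.08 SD for mildly unequal loss, to .23-.36 SD in a deliberately extreme case.

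**What to change.** For each composite, make the primary test one likelihood-based mixed model with B and C as outcomes. Terms: arm, visit, arm by visit, the Assessment A composite and its interaction with visit. Use Kenward-Roger degrees of freedom, and include everyone with a baseline and any follow-up score, as randomised. Keep the two-visit ANOVAs as supporting analyses.

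- **Multiplicity.** Because .025 is .05/2 for two composites, testing both visits at .025 would make four tests. Name arm at B as the test at .025, and test arm at C only if B is significant, or label C as supporting.
- **Missing data.** State the missing-at-random assumption. Add a sensitivity analysis for the 4 to 6 people with no B or C score, whom the model does not recover.
- **Consistency.** Make the sample size justification and the Data Analysis Plan name the same analysis.
- **Covariates (secondary).** Replace the conditional rule with a small set fixed in advance. The reason is prespecification, not power: at N=30, f=.16 and ρ=.5, covariates that explain nothing beyond baseline lower power from 26% to 25% (one) or 22% (four).

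The cost is SAP wording, standard software and one degree of freedom per visit; no new data are needed. There is little gain if ρ is about .9, and no protection if loss depends on unseen C scores.
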